- **% continuing** – those with no gap in therapy greater than 30 days and who do not begin a new treatment during the study period.
- **% discontinuing** – those with gap in therapy greater than 30 days and who do not begin a new treatment.
- **% with treatment interruption** - those with gap in therapy greater than 30 days but who eventually continue the original treatment (have an additional administration or refill) and do not switch or augment therapy during the study period.
- **% switching** – those with gap in therapy greater than 30 days and who begin a new treatment.
- **% augmenting** – those who begin a new treatment but continue using the original treatment (have an additional administration or refill) and do not have a gap in therapy greater than 30 days of their original treatment.
- **Overall and aRCC Follow-Up Costs:** Total and RCC-specific pharmacy, medical costs from aRCC therapy index through follow-up period (costs summarized as: mean, median costs per patient and costs per patient per month).

PFIZER CONFIDENTIAL

- **Overall and aRCC Follow-Up Utilization:** Total and RCC-specific inpatient, ER, outpatient visits from aRCC therapy index through follow-up period (utilization will be summarized as: mean, median utilization per patient and utilization per patient per month).
- **Overall landmark survival:** Using Optum claims and PanTher data, landmark survival will be described and compared over follow-up time periods (3, 6, 12 months).
- **Mean/Median Survival:** Using Optum claims and PanTher data median survival time will be described and compared over follow-up time periods determined after feasibility assessments of cohorts of interest.

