6.3. Variables

6.3.1. Treatment Pattern Variables

Table 5. Treatment Pattern Variables

Variable	Operational definition
Initial (1L)Treatment Regimen	The first treatment regimen prescribed following a primary and secondary diagnosis of advanced/metastatic disease.
Monotherapy vs Combo therapy	Categorical: Yes/No Combo therapy is defined by a second medication filled on or within 30 days of the original medication and the original medication is filled subsequently. CCI [REDACTED]
Time to FL treatment received	Continuous: days Length of time (days) from the first mRCC diagnosis (first ever secondary malignancy code associated with RCC) to first line therapy prescription.
Treatment discontinuation date (by LoT) – to be used for time to treatment failure (TTF) and time to next line of therapy	Date Treatment discontinuation indicating the end of LOT will be identified as the earliest of: 
For oral therapy: to the run-out date of the last prescription (ie, date of last prescription plus days supply) in the same treatment line.For non-oral therapy: 30 days after the last observed prescription/administration prior to at least a 30 day gap in therapy of all agents included in the first line of therapy.1 day before a new prescription/administration date, whichever occurred earlier.For multiple drug regimens: the above would be triggered by the last prescription/administration in the regimen.Death.End of enrollment.
Days of continuous treatment (by LoT)	Continuous: days The duration of each LOT will be measured from the first prescription or administration of line of therapy medication(s) to the end of the line of therapy, allowing for 30 day allowable gaps in therapy.
Treatment Continuation	Categorical (Y/N) There is no >30 day gap (ie, persistent treatment) for the index medication during follow-up period.

PFIZER CONFIDENTIAL

[REDACTED]

Variable	Operational definition
Treatment Interruption	Categorical (Y/N) At least one instance of >30 day gap (ie, non-persistent treatment) for the index medication during follow-up period or LOT followed by resuming therapy (not mutually exclusive with switch, augment, discontinuation, but a sub-group within LOT).
Interrupted treatment duration	Continuous: days Time from index medication to treatment discontinuation for those within treatment interruptions (>30 day gaps). Represents the time between index and end of last treatment, including any treatment gaps.

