6.4. Data Sources

Results will be replicated to the extent possible across various real world databases in order to confirming and validate results across data sources. At the start of the study, four databases will be evaluated. IBM's Truven MarketScan Commercial, Optum Clininformatics, the IMS PharMetrics claims databases and The PanTher (which has both Humedica EMR data including EMR notes linked to Optum claims). After population sizes are assessed in the various databases, sub-analysis for populations with adequate patient data will be clarified in an amendment to this protocol.

[figure not shown]
Optum Clininformatics:

Optum Clininformatics has access to a proprietary research database containing claims and enrollment data dating back to 1993 with the opportunity to link patient and physician survey data to pharmacy and medical claims, medical record data, socioeconomic measures, and clinical laboratory results on over 123 million lives. Underlying information is geographically diverse across the United States, and is updated frequently. The research activities utilize de-identified data from the research database except in limited instances where applicable law allows the use of patient identifiable data.

Claims for pharmacy services are typically submitted electronically by the pharmacy at the time prescriptions are filled. The claims history is a profile of all outpatient prescription pharmacy services provided and covered by the health plan. Pharmacy claims data include drug name, dosage form, drug strength, fill date, days of supply, financial information, and de-identified patient and prescriber codes, allowing for longitudinal tracking of medication refill patterns and changes in medications. Pharmacy claims are typically added to the research database within 6 weeks of dispensing.

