Medical claims or encounter data are collected from all available health care sites (inpatient hospital, outpatient hospital, emergency room, physician's office, surgery center, etc.) for virtually all types of provided services, including specialty, preventive and office-based treatments. Medical claims and coding conform to insurance industry standards. Claims for ambulatory services submitted by individual providers, eg, physicians, use the HCFA-1500 format. Claims for facility services submitted by institutions, eg, hospitals, use the UB-82 or UB-92 format. Medical claims include: multiple diagnosis codes recorded with the ICD-9-CM diagnosis codes; procedures recorded with ICD-9-CM procedure codes, Current Procedural Terminology (CPT), or Health Care Financing Agency (HCFA) Common Procedure Coding System (HCPCS) codes; site of service codes; provider specialty codes; revenue codes (for facilities); paid amounts; and other information. Typically, facility claims do not include any drugs administered in hospital. Approximately 6-9 months following the delivery of services is required for complete medical data, therefore patients will be followed for this additional time period. In summary, the analysis window will include data from 24 months pre index date, and 24 months post index date.

PFIZER CONFIDENTIAL

Integrated Optum E.H.R and Claims (PanTher)

Integrated Optum E.H.R. (formerly Humedica) clinical data and Optum Clininformatics administrative claims data (United enrollees) are included in the Optum PanTher Database. Estimated to be approximately 15% of the Optum Claims lives are represented in this database. This asset combines the clinical specificity of the Optum E.H.R. data with the administrative claims data which includes cost data, pharmacy fill data, and enrollment time periods among other things.

The Optum EHR database has broad geographic representation and includes patient demographic and clinical information, including diagnosis, medications, labs, procedures, microbiology and biomarkers. Optum EHR also extracts data from physician notes using industry-leading Natural Language Processing (NLP).

[figure not shown]

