The Optum EHR database includes patient records from multiple EMR systems which capture data from different sites of care and a full spectrum of inpatient and outpatient treatment (eg, both Written Prescription and Inpatient-Administered medications). Records are completely de-identified and are fully compliant with the Health Insurance Portability and Accountability Act (HIPAA). Data is sourced from large Integrated Delivery Networks (IDN) with over 60% of patients having both outpatient and hospital information. The remainder of the patients are from large multi-specialty physician practices.

Outpatient laboratory test results are available for subpopulations of the research database. Standard Logical Observation Identifiers Names and Codes (LOINC) coding is used to define specific tests and results. Test results data can be linked to the other health care utilization and pharmacy claims data in the research database. Results included in the database are typically from blood-based tests (eg, low-density lipoprotein, glycated hemoglobin levels) that are sent for processing to two of the largest laboratory facilities in the country. Data are available for approximately 30-40% of members who were administered the test, depending on the test.

Truven Marketscan Commercial:

The MarketScan data warehouse is a family of databases from commercially insured lives. Pfizer licenses the following data sources: healthcare claims, hospital drug/discharge information with links to claims data and Medicare Supplemental files. The Truven Health MarketScan Research Databases reflects the combined healthcare service use of individuals covered by Truven Health clients (including employers, health plans, and hospitals) nationwide. Truven Health builds databases comprise the healthcare experience of the clients' covered populations, as well as information about the populations themselves and the providers that serve them. MarketScan Research Databases provide detailed cost, utilization, and outcomes data for healthcare services performed in both inpatient and outpatient settings. In the claims databases, the medical services are linked to outpatient prescription drug claims and person-level enrollment data using unique enrollee identifiers.

PFIZER CONFIDENTIAL

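### In the Optum Clininformatics claims analysis, the >30-day gap rule makes no allowance for drugs given in hospital, so some continuously treated patients can be scored as interrupted or discontinued

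*Combined protocol and SAP*

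**What the plan says.** Section 6.4 describes what Optum Clininformatics can see. On medical claims it states: "Typically, facility claims do not include any drugs administered in hospital". On pharmacy claims it states: "The claims history is a profile of all outpatient prescription pharmacy services provided and covered by the health plan". A study drug supplied during an admission would therefore normally appear in neither stream.

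The treatment-pattern outcomes depend on those streams. Section 6.1 (and Table 7) defines discontinuing patients as "those with gap in therapy greater than 30 days and who do not begin a new treatment". Table 5 defines interruption as "At least one instance of >30 day gap (ie, non-persistent treatment) for the index medication during follow-up period or LOT followed by resuming therapy". For the end of a line, which feeds TTF, Table 5 takes oral therapy "to the run-out date of the last prescription (ie, date of last prescription plus days supply) in the same treatment line" and non-oral therapy as "30 days after the last observed prescription/administration prior to at least a 30 day gap in therapy of all agents" in the first line. For multi-drug regimens, the last prescription or administration of any agent sets the end.

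No section credits, bridges or censors inpatient days. Section 6.9 warns of errors in days supply and dosage but does not mention drugs given in hospital.

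The other databases are described differently. The Optum EHR data in PanTher capture treatment in both settings ("eg, both Written Prescription and Inpatient-Administered medications"). MarketScan is said to come with hospital drug information linked to claims. PharMetrics is described as holding prescription and outpatient-administered drugs, with inpatient-administered drugs not named. Nothing says that the PanTher or MarketScan inpatient records will be used to fill gaps.

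**The concern.** The plan states a limit on what the claims record and then defines Objective 3 outcomes as if an absent record meant absent treatment. For a patient who stays on treatment, a missing record can only lengthen the apparent gap. The error falls on hospitalised patients and depends on the dosing interval and on the number of agents, so it could tilt the descriptive comparison between regimens. It is also separate from claims lag, because these records do not arrive later. Interruption, discontinuation and TTF are the outcomes meant to show unmet need, so artefactual failures matter.

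**Working it through.** The plan states no misclassification rate, so there is no figure to reproduce. The check applies the plan's own day counts.

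**Inputs from the documents.** The threshold is more than 30 days. Table 9 imputes 28 days for nivolumab and durvalumab; 21 for ipilimumab, pembrolizumab and atezolizumab; 14 for avelumab and bevacizumab; and 7 for temsirolimus.

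**Infused drugs, doses on schedule.** With imputed supply s and k consecutive unseen doses, the gap from imputed run-out is k × s.
- One unseen dose gives 28, 21, 14 or 7 days. None exceeds 30.
- Unseen doses needed to pass 30: two for the 28-day drugs (56) and the 21-day drugs (42), three for the 14-day drugs (42), five for temsirolimus (35).
- If the gap runs from administration plus 30 days, it is (k+1) × s − 30, and the numbers needed are two, two, four and eight.
- If it is read as the raw interval between administrations, one unseen dose gives 56 or 42 days and is flagged for the 28- and 21-day drugs.

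The plan does not settle which of these origins applies.

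**Infused drugs with delay.** From imputed run-out, one unseen dose is flagged once the total delay reaches 31 − s days: 3 for a 28-day drug, 10 for a 21-day drug, 17 for a 14-day drug. For example, take doses on days 0, 31 (in hospital, unseen) and 62 with 28 imputed days. The gap is 62 − 28 = 34 days, or 62 − 30 = 32 days from administration plus 30. Under the non-oral rule in Table 5 the line ends on day 30, although no dose was missed.

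**Oral drugs.** If the hospital supplies the drug, gap = inpatient days + other refill delay. The shortest stay that triggers a flag is 31 days with no other delay, 21 with 10 days, 11 with 20 days and 6 with 25 days. For example, take a 30-day fill on day 60 (run-out day 90), a 20-day stay from day 75 to day 95, and a refill on day 123. The observed gap is 33 days. The patient's own supply lasted to about day 110, so the true gap is 13 days.

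**Illustrative size, on assumed inputs.** The documents give no admission rate, length of stay, delay or unseen share. Assume 0.06–0.12 admissions per month and mean stays of 6–10 days. The share of time in hospital is then 0.06 × 6 / 30.4 = 1.2% to 0.12 × 10 / 30.4 = 3.9%. If infusions fall evenly over time and every one due during a stay is given there, about 1.2–4% of doses are unseen. That is an upper bound for those admission assumptions.

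The model simulates single-agent patients who never stop over 182 days, with an exponential delay per cycle and doses unseen at random. The gap is counted from imputed run-out.

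| Imputed days | Mean delay | 0% unseen | 1.2–4% unseen |
|---|---|---|---|
| 28 | 4 days | 0.2% | about 5–14% |
| 21 | 4 days | 0.3% | about 3–8% |
| 28 or 21 | none | 0% | 1% or less |

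The origin of the gap matters too. At 5% unseen, counting from administration plus 30 days lowers the 28-day figure from 17% to 14% and the 21-day figure from about 10% to 2–3%.

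For oral 30-day fills under the same admission assumptions and mean refill delays of 4–7 days, about 0.6–11% are flagged as written, against 0.2–5% with inpatient days removed.

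**The case against.** The strongest reply is that the rule is already tolerant. Dispensed oral supply and imputed infusion cover run on through a stay, and a further 30 days is then allowed. A reader might infer that every inpatient day is counted as untreated; the definitions do not support that. From imputed run-out, a single unseen dose given on schedule never crosses the threshold.

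A reader might also infer that infused immuno-oncology regimens are always hit hardest. That does not follow either. Table 5 requires all first-line agents to lapse, so outpatient axitinib fills can bridge an unseen infusion in the IO+TKI cohort. Protection is weaker for nivolumab plus ipilimumab, where both agents are infused and could be unseen together. The simulation covers single agents only.

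Nor does the source sentence cover all four databases. It describes Optum Clininformatics, and PanTher and MarketScan are said to hold inpatient or hospital drug data.

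Finally, no section shows that treatment continues in hospital. Crediting inpatient days can erase a real interruption. Suppose a 28-day drug is given on day 0, the patient is in hospital on days 50–60, and the next dose is on day 85. The gap is 57 days. A rule that restarted the 30-day count at discharge would see only 25 days and miss it.

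These points limit scope and size and argue against making an inpatient credit the primary rule. They do not supply the missing provision. The study is descriptive and section 6.9 disclaims causal inference, but that does not correct a misclassified outcome.

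**Conclusion.** The concern holds in a limited form. In the Optum Clininformatics analysis, some patients who stayed on treatment can be scored as interrupted or discontinued, with TTF shortened, because the gap rule is silent on treatment the claims typically do not show. It takes a stay or unseen dose added to an existing delay, or several consecutive unseen infusions. The same may apply to PharMetrics, but its description does not settle that.

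The size cannot be derived from the documents. The ranges of about 5–14% (28 imputed days) and 3–8% (21 imputed days) rest on an assumed 1.2–4% of doses unseen, a mean delay of 4 days, a single agent and a gap counted from imputed run-out. The true effect is near zero if study drugs are rarely given in hospital or doses run on schedule. This is a cheap improvement to core outcomes; it does not invalidate the analysis.

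**What to change.** - Keep the current rule as primary, and state in Table 5 the date from which an infused drug's gap is counted.
- In Table 5 and section 6.7, add a sensitivity analysis for the claims databases without inpatient drug records. It extends supply by each overlapping inpatient stay, using the admissions behind the length-of-stay variable in Table 8. Report continuation, interruption, discontinuation and TTF both ways, by regimen.
- In PanTher, use the EHR inpatient-administered records to fill in doses, and report the share that claims alone miss. PanTher holds an estimated 15% of Optum claims lives, so this estimate may be imprecise.
- Name the limitation in section 6.9.

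The cost is a little more programming and no new data source. The credited version can hide, or date later, a true interruption that began during an admission, so the two versions should be read as bounds.

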6.2.1. Inclusion Criteria

Subjects will be selected irrespective of their survival status. Patients must meet all of the following inclusion criteria to be eligible for inclusion in the study:

- **Index date:** The first prescription or administration of one of the medications indicated for advanced RCC recorded in the database between April 2018-March 31, 2019, among those with no aRCC treatment in their history.
- Age 18 years or older in the year of the index first line therapy prescription.
- 2 or more RCC diagnoses (ICD-9: 189.0; ICD-10: C64.1, C64.2, C64.9) at least 30 days apart, in the 1 year prior to the index date until 30 days post index date.

PFIZER CONFIDENTIAL

- 2 or more code for secondary malignancy codes indicating possible diagnoses for metastatic disease at least 30 days apart, in the 1 year prior to the index date until 30 days post index date. (ICD-9: xx-199.xx; ICD-10: C77-C79, except ICD9: 198.0 Secondary malignant neoplasm of the kidney and ICD10: C79.0 Secondary malignant neoplasm of the kidney and renal pelvis).
 - CCI [REDACTED]
- Continuous enrollment from 12 months prior to the index date. Patients will be required to have continuous enrollment from their index date until the end of the available data. This will allow for sub-analysis of cohorts with 3 months, 6 months and 12 months of available data.

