The MarketScan Commercial Database contains the healthcare experience of privately insured individuals. Coverage is provided under a variety of fee-for-service, fully capitated, and partially capitated health plans, including preferred provider organizations, point of service plans, indemnity plans, and health maintenance organizations.

The Enrollment Detail Table provides a single record per month of enrollment for each enrollee, with detailed demographic information.

Claims are not included in the database until they have been adjudicated; there is a lag of approximately six months after the close of a calendar year or a quarter between services provided and their inclusion in the Research Databases. However, the Early View Database has a 90-day lag that includes paid amounts for 100 percent of prescription drugs, approximately 85 percent of physician office visits, and approximately 70 percent of hospital claims. The MarketScan Early View Database includes all of the components found in the standard MarketScan Commercial and Medicare Supplemental Databases. It includes standardized inpatient, outpatient, pharmaceutical, and health-plan enrollment data. The MarketScan Early View Database captures healthcare services incurred up to 90 days before data release and includes only adjudicated claims. However, the medical component of care for some patients will not be complete, since some claims (particularly inpatient claims) take longer to be adjudicated. Because this study is examining only comorbidities prior to and treatments during or prior to glasdegib initiation fully adjudicated claims are not required and all available data will be used including Commercial, Medicare Supplemental, and Early View Databases.

[figure not shown]
Pharmetrics Plus

The PharMetrics Plus database is comprised of fully adjudicated medical and pharmacy claims. Specifically, it contains a longitudinal view of inpatient and outpatient services, prescription and office/outpatient administered drugs, costs and enrollment information. With PharMetrics Plus, you can track an enrolled patient across all sites of care: hospital, specialist, emergency room, pharmacy, primary care, ambulatory, and more.

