There are over 140 million unique enrollees with both medical and pharmacy benefits. The enrollee population in the PharMetrics Plus database is generally representative of the under 65 commercially insured population in the US with respect to both age and gender. We have over 10 million enrollees who are over 65 years of age. Longitudinal enrollment range of individuals in the database on average is 36 months and more than 42 million patients have 3 or more years of continuous enrollment.

The PharMetrics Plus database offers a diverse representation of payer types, provider specialties, geographic granularity and linking capabilities. Patient region and state are standard patient variables and zip3 is optional and available for a subset of patients. Provider identification is an optional variable and available for a subset of providers using the National Provider Identifier. Patient linking is achieved by leveraging IQVIA's patented

PFIZER CONFIDENTIAL

technology for the subset of patients assigned a unique, encrypted patient key in multiple databases. Please note that there can be limits to the provisioning of the combination of some variables when linking is enabled.

Commercial insurance is the most frequent plan type captured for the enrollee population but other types are also found, including Commercial Medicare, Commercial Medicaid, Self-Insured, Indemnity and Others. In addition to standard fields such as inpatient and outpatient diagnoses and procedures, retail and mail order prescription records, PharMetrics Plus has detailed information on the pharmacy and medical benefit (copayment, deductible), the inpatient stay and provider details (provider specialty included in all extracts). Economic variables include the negotiated rate between the plan and providers (allowed) and the actual amount paid by health plans to the provider for all services rendered. Charge amount is also available for a subset of claims. Other data elements include dates of service, demographic variables (age, gender, and geographic region), product type (eg, HMO, PPO), payer type (eg, commercial), and start and stop dates of health plan enrollment. All data are HIPAA compliant to protect patient privacy.

While the most recent release of the PharMetrics Plus database is typically used to create all client deliverables, there may be a 4-6 month lag with newer claims largely owing to the typical processing time for claims adjudication mentioned above.

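### Infusion claims mature months later than pharmacy claims, and no eligibility or outcome rule sets a claims-complete date, so unloaded infusions can be scored as stopped or interrupted IO treatment

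*Combined protocol and SAP*

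**What the plan says.** Section 6.4 gives different loading times by claim type. For Optum Clininformatics, "Pharmacy claims are typically added to the research database within 6 weeks of dispensing". For medical claims, "Approximately 6-9 months following the delivery of services is required for complete medical data, therefore patients will be followed for this additional time period". The sentences that follow set an analysis window of 24 months either side of index.

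For MarketScan, Early View is said to hold "paid amounts for 100 percent of prescription drugs, approximately 85 percent of physician office visits, and approximately 70 percent of hospital claims". The plan nevertheless concludes that "fully adjudicated claims are not required and all available data will be used including Commercial, Medicare Supplemental, and Early View Databases". The reason given concerns comorbidities and treatments up to the start of glasdegib, a drug that is not in Table 4.

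In Table 4 every TKI is oral and every IO agent is an injection. Section 6.1 (Analysis 3) and Tables 5 and 7 apply one threshold, a gap above 30 days, to all drugs. Table 5 ends a non-oral line "30 days after the last observed prescription/administration prior to at least a 30 day gap in therapy" of all its agents, and lets the last agent seen set the end of a multi-drug regimen.

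On observation time, section 6.2.1 says "Patients will be required to have continuous enrollment from their index date until the end of the available data". It presents this as the basis for the 3-, 6- and 12-month cohorts, and section 6.2.2 sets a 3-month minimum. Section 6.1 fixes outcome follow-up at 6 months, with other lengths as sub-analyses. Section 6.6 plans periodic regeneration of tables at database refreshes. No section states an extraction date, a run-out period or censoring for claims maturity.

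**The concern.** A treated patient whose recent infusions have not yet loaded looks the same as one who has stopped. In a claims file infusions would normally arrive as medical claims and oral fills as pharmacy claims. This is an inference, but a reasonable one, since Table 8 separates drug costs by medical and pharmacy claim. The slower feed therefore carries the IO exposure record and the faster one the TKI record, while the same gap threshold judges both.

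Time to treatment failure, discontinuation and interruption are key outcomes, and section 6.1 uses them to show unmet need with current regimens, naming ipilimumab/nivolumab. Loading delay would make IO monotherapy and IO+IO look less persistent than oral TKI. Section 6.9 does not list this among the limitations. Section 6.4 treats replication across databases as validation, so agreement between two sources that share the artefact could be misread as confirmation.

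**Working it through.** The plan states no sample size, event count or misclassification rate, so there is no figure to reproduce. Three checks were made.

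**1. How much follow-up is mature at a given extraction date**

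Inputs: index window 1 April 2018 to 31 March 2019 (section 6.2.1, 365 days); Optum lags of 42 days for pharmacy claims and 6 or 9 months for medical claims (section 6.4). Assumed: uniform accrual, and the extraction dates.

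Latest mature index date = extraction date − lag − follow-up length. Share mature = days from 1 April 2018 to that date, inclusive, divided by 365.

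For 6-month follow-up and extraction on 4 October 2019 (the protocol version date):
- Oral: 23 February 2019, 329/365 = 90%.
- Infused, 6-month lag: 4 October 2018, 187/365 = 51%.
- Infused, 9-month lag: 4 July 2018, 95/365 = 26%.

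The last patient's 6 months end on 30 September 2019, so on that extract the whole index window has had 6 months elapse, mature or not.

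| Extraction (assumed) | Follow-up | Oral | Infused, 6-month lag | Infused, 9-month lag |
|---|---|---|---|---|
| 4 Oct 2019 | 6 months | 90% | 51% | 26% |
| 31 Dec 2019 | 6 months | 100% | 75% | 50% |
| 31 Mar 2020 | 6 months | 100% | 99.7% | 75% |
| 30 Jun 2020 | 6 months | 100% | 100% | 99.7% |
| 30 Jun 2020 | 12 months | 100% | 75% | 50% |

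Section 6.1 leaves the index window open to the present instead of closing it on 31 March 2019. On that reading more follow-up would be immature.

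**2. How many missing infusions trip the rule**

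With dosing interval s (Table 9) and m consecutive missing claims, the gap is (m+1)s minus the covered days.
- Nivolumab, s = 28, counted from end of supply: one missing, 56 − 28 = 28 days; two missing, 84 − 28 = 56 days.
- Ipilimumab or pembrolizumab, s = 21: one missing, 42 − 21 = 21 days; two missing, 63 − 21 = 42 days.
- Counted from administration plus 30 days, two are again needed: 84 − 30 = 54 and 63 − 30 = 33 days.
- Avelumab, s = 14, needs three (56 − 14 = 42) or four (70 − 30 = 40).
- Only if the gap is counted from the administration date itself does one missing claim suffice for the 21- and 28-day drugs.

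At the end of the data, a nivolumab patient is flagged 28 + 31 = 59 or 30 + 31 = 61 days after the last visible infusion, well inside a 6-9 month immature tail. A missing tail scores as discontinuation. Interruption needs a later visible claim, so it arises from patchy loading.

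**3. Illustration for Early View**

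Assumed: the stated shortfalls (15% office, 30% hospital, 0% prescriptions) apply to each infusion claim, and true continuation is 60%. The chance that the last two infusions are both missing is:
- independent claims: 0.15² = 2.3% or 0.30² = 9.0%;
- missingness fully clustered by patient: 15% or 30%.

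Apparent IO continuation = 0.60 × (1 − that chance): 58.7% or 54.6% if independent, 51% or 42% if clustered. The loss is 1.4 to 18 percentage points for IO and none for oral TKI.

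**The case against.** The best defence is that the plan sees the lag and allows for it. Outcome windows are fixed, so added observation after a window is genuine run-out. If the 24-month post-index window were honoured, a 6-month outcome would have 24 − 6 = 18 months of run-out and a 12-month outcome 24 − 12 = 12, both above 9. This stands as far as it goes: the lag is not ignored, and only windows that overlap the immature tail are affected. But the 24 months appear only in the data-source description. Sections 6.2.1 and 6.2.2 admit patients with as little as 3 months of data, and no outcome rule excludes the immature months. Analysis 1's treated period has no fixed length, and a 2-year sub-analysis is also foreseen.

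Other limits also stand:
- IO+TKI is largely protected, because the line stays open while TKI fills are visible.
- PanTher adds EHR records of administered drugs, which reduces the effect.
- In Optum the contrast is one of degree: a 42-day pharmacy lag also exceeds 30 days, so some oral patients near extraction could show false gaps.

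A reader might go further in three ways that the documents do not support.
- That PharMetrics has the same differential bias. The plan says only that "there may be a 4-6 month lag with newer claims", does not split this by claim type, and describes the claims as fully adjudicated.
- That 42-57% of persistent IO patients would be misclassified. This is the chance of two consecutive misses among 8 to 12 infusions at 30% missingness each. It applies an Early View hospital-claim rate to Optum, holds it constant while claims mature, and assumes treatment throughout the tail.
- That drugs given in hospital belong to this problem. "Typically, facility claims do not include any drugs administered in hospital" describes permanent non-capture, which no cut-off date can repair.

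**Conclusion.** The concern holds in a limited form. For Optum and MarketScan Early View, the plan's own figures show a slower or less complete feed for medical than for pharmacy claims, and no rule prevents immature months from being scored. The likely direction is against IO monotherapy and IO+IO relative to oral TKI.

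The size cannot be fixed from the documents, because it turns on the unstated extraction date. An extract near the protocol date would leave about half to three quarters of the index window immature for infused 6-month outcomes, against about a tenth for orals. An extract around mid-2020 would settle the 6-month analysis, but would leave a quarter to a half immature for infusions at 12 months. These are shares of follow-up exposed to the problem, not shares of patients misclassified. The 1.4 to 18 point range is an Early View illustration resting on assumed missingness and 60% true continuation.

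**What to change.** In sections 6.1, 6.2.1 and 6.4:
- State the extraction date and a claims-complete date for each database. For Optum, use extraction minus 9 months. For the others, derive it from the stated lag, without subtracting that lag again where the release already contains only adjudicated claims.
- Require the 3-, 6- or 12-month window to end by that date, and end treatment follow-up there for all regimens, oral and infused.
- Censor, and do not score as discontinued, any patient whose supply plus 30-day gap window runs past it. State from which date the gap is counted.
- Exclude Early View from duration and persistence outcomes, or use it only as a sensitivity analysis, and replace the rationale about glasdegib.

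The cost is protocol wording, one date parameter per database, and some usable follow-up. With a 9-month lag, the last patient indexed on 31 March 2019 has mature data from about 30 March 2020 (3 months), 30 June 2020 (6 months) and 31 December 2020 (12 months). An Optum extract on 30 June 2020 would therefore keep about 50% of the index window for the 12-month cohort. Later refreshes, which section 6.6 already plans, would recover the rest.
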